Version 3.0	06-MAR-2023	1. Update to participant exclusion criteria 2. Clarification of the last day of study participation 3. Clarification about the schedule of activities
Version 4.0	23-OCT-2023	1. Update to method to photograph target areas 2. Update to details of study population in Synopsis and Section 5

1. PROTOCOL SUMMARY

1.1. Synopsis

Title: Efficacy of a skin protectant textile for the management of skin fold conditions.

Study Description: Chronic irritation at skin-on-skin contact areas such as skin folds may be caused by moisture, heat, friction, lack of air circulation, incontinence, or poor hygiene, and can result in inflammatory conditions. These conditions may be complicated by fungal and/or bacterial infections. Commonly affected areas include the groin, inner thigh, armpits, the areas between the buttocks, the underside of the breasts, or the abdominal panniculi.¹ Signs and symptoms include erythema, crusted or oozing skin, itching, burning, pain, and malodor. Important risk factors include obesity, malnourishment, immobility, and diabetes, with the elderly or bed-ridden individuals and infants being commonly affected.

DriGo-HP™ (formerly known as the “Stay Fresh® Skin Fold Management Textile”; henceforth referred to as “skin protectant textile [SPT]”) is used in skin folds to provide moisture management, friction reduction, and odor control. It is made from a soft, thin, smooth polyester textile, which when placed within skin folds helps to wick moisture away from the skin fold. The textile contains up to 0.3% hydrogen peroxide (H₂O₂), which is released slowly over time. This concentration is safe for the skin and prevents growth of common bacteria, including *Escherichia coli* (*E. coli*) and Methicillin-Resistant *Staphylococcus aureus* (MRSA), in the fabric. The reduction in moisture and control of bacterial growth results in odor control in the skin fold. The SPT is intended to be used between skin folds and in other skin-to-skin contact areas, to provide moisture and odor management, and to reduce friction.

This study will evaluate the efficacy of the SPT to manage erythema, maceration, denudation, satellite lesions, pain, itching, burning, moisture, and odor associated with skin folds (henceforth together referred to as “skin fold conditions”). Participants will be patients with skin fold conditions, which will be treated with the SPT. Healthcare providers (HCPs) will apply the SPT to the participants’ skin folds and other skin-on-skin contact areas (henceforth referred to as “target area[s]”). An independent licensed clinician with experience in identifying and treating skin fold conditions (henceforth referred to as “third-party clinician”), will use photographs of the target areas to assess the status of erythema, maceration, denudation, and satellite lesions in the target areas when the SPT is first applied (Day 0), and on Days 1, 3, and 5 (or the last day of study participation [ie, fully healed target area(s)]), during SPT changes. The PI or qualified designee will take photographs of the target areas and assess moisture and odor in these areas. Participants will provide their impressions of pain, itching, and burning in the target area(s) on the same days as the skin fold condition photography. In addition, the study will include feedback from the HCPs about the SPT and overall experience of the participants with the SPT.

Phase:	Post-market
Primary Objective:	To evaluate the efficacy of the SPT to improve skin fold conditions.
Secondary Objectives:	
1. To gather PI or qualified designee's assessment of moisture control in the target areas.2. To assess HCP feedback on the SPT.3. To assess the overall participant experience with the SPT.
Primary Endpoint:	
1. Improvement in skin fold conditions such as erythema, maceration, denudation, satellite lesions, odor, pain, itching, and burning over five days of treatment.
1a. Likert scales developed for erythema, maceration, denudation, and satellite lesions. Scoring of the target area(s) done by a third-party clinician using the Likert scale(s) and photographs taken by the PI or qualified designee on Day 0, and on Days 1, 3, and 5, during SPT changes.1b. Assessment of odor in the target area(s) on Day 0, and on Days 1, 3, and 5, during SPT changes, using a Likert scale.1c. Participant assessment of discomfort (pain, itching, and burning) using a visual analogue scale (VAS) on Day 0, and on Days 1, 3, and 5, during SPT changes. Participants will also be asked to identify the most prominent type of discomfort in the skin fold: pain, itching, or burning.
Secondary Endpoints:	
1. PI or qualified designee survey responses for moisture in the target area(s) on Day 0, and on Days 1, 3, and 5, during SPT changes, using a Likert scale.2. HCP survey responses on Day 5, regarding their feedback about the SPT, using a VAS.3. Participant responses on Day 5, regarding their experience with the SPT, using a VAS.
Note:	All endpoint-related activities planned for Day 5 will be carried out for the last day of study participation (ie, fully healed target area[s]) if it occurs before Day 5.
Study Population:	Number of target areas, N = 119. Participants can be the source of up to two target areas, and each target area can have more than one skin fold condition. Per the assessment of the PI or qualified designee, the skin fold conditions of the participants must be anatomically distant enough to allow the participants to make an objective assessment of discomfort (pain, itching, and burning) in each target area. A participant may be re-enrolled using a new participant study identification (ID) number for another set of up to two target areas at a different location. The target areas must be anatomically distant (per the assessment of the PI or qualified designee), as described above.

Inclusion criteria

Individuals who meet all of the following criteria will participate in this study:

- Individuals \geq 18 years of age.
- Individuals who have evidence of one or more of the following skin fold conditions: erythema, maceration, denudation, satellite lesions, pain, itching, burning, moisture, and odor.
- Individuals whose treatment plan permits assessment of the skin fold condition(s) for up to six days.

Exclusion criteria

Individuals who meet any of the following criteria will not be eligible to participate in this study:

- Individuals whose target area(s) are being managed with topical treatments such as antibiotics, antifungals, ointments including skin protectants, anti-itch products, anoperineal dressings or absorbent pads (eg, ARD®).
- Individuals with a known allergy or sensitivity to the ingredients in the SPT, such as the fabric or H₂O₂, as well as the tape that may be used to secure the SPT.
- Individuals who are pregnant or are breastfeeding.

Description of Sites/Facilities At least one acute care facility (non-intensive care unit [non-ICU]) will be involved in the study. If more than one facility is involved, enrollment will be competitive.

Enrolling Participants: Up to six days.

Participant Duration: Up to six days.

Note:

Two interim analyses will be conducted to confirm that participants being enrolled present a balanced distribution of skin fold conditions.

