5.3. Strategies for Recruitment and Retention

The PI at the study site will recruit potential participants from the current patient population being treated at the facility who satisfy the inclusion/exclusion criteria. The PI will inform the participants that they are free to withdraw from the study at any time and that it will not affect their treatment in any way. For this study, advertisements of any kind or a database to look up potential participants will not be used.

Retention will ideally be managed by targeting participants who are anticipated to require at least five days of SPT treatment.

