5.4 Early Withdrawal and Replacement

Participants whose skin fold conditions are healed prior to Day 5 will be considered to have complete data.

Participation in the study may end at several critical points:

- Participant withdraws from the study for any reason, including when the target area(s) have not healed but the participant is discharged due to resolution of the medical condition for which the participant was hospitalized.
- Participant is not compliant with study procedures.
- Participant presents with adverse event(s) such that, in the opinion of the PI, it is in the best interest of the participant to discontinue study participation.
- Protocol violation requiring discontinuation of use of the study product(s).

Based on the above reasons, if any participant withdraws from the study or is dismissed, additional participant(s) will be recruited such that the total number of target areas included in the study will be 119.

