8.3. Populations for Analyses

The analyses will be performed on the intent-to-treat population, which consists of all participants who were qualified for entry criteria and adhered to the protocol, meaning completing five days of treatment with complete data on assessment of skin fold conditions, as well as responses on discomfort and overall experience with the SPT.

No per protocol, safety, or other analysis groups are planned.

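### The availability criterion sets no explicit minimum stay, so areas of patients already expected to leave before Day 5 can be enrolled, then kept if healed and replaced if not

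*Combined protocol and SAP*

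**What the plan says.** The availability criterion appears in the Synopsis and again in 5.1: "Individuals whose treatment plan permits assessment of the skin fold condition(s) for up to six days". Neither place gives a lower limit. The Schedule of Activities (1.2) puts the last assessment on Day 5, which is the sixth calendar day counting Day 0. The setting is at least one acute care facility outside intensive care (Synopsis).

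The only other text on who will stay long enough is in 5.3: "Retention will ideally be managed by targeting participants who are anticipated to require at least five days of SPT treatment".

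Section 5.4 treats two kinds of early ending differently:
- Healed: "Participants whose skin fold conditions are healed prior to Day 5 will be considered to have complete data". Section 6.3 agrees, provided the Day 5 activities are done on the last day.
- Not healed: participation may end with withdrawal, "including when the target area(s) have not healed but the participant is discharged due to resolution of the medical condition". For withdrawals and dismissals, "additional participant(s) will be recruited such that the total number of target areas included in the study will be 119".

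Section 8.1 repeats the replacement rule and specifies that the final 119 areas have complete data. Section 8.3 defines the only analysis population. It is labelled intent-to-treat but requires "completing five days of treatment with complete data on assessment of skin fold conditions". No other analysis set is planned, and 8.8 drops missing ratings without imputation.

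**The concern.** Up to six days is, on its face, an upper bound. A treatment plan that allows two or three days of assessment can be said to meet it. A site applying the criterion literally could enrol a patient whose discharge is already scheduled for Day 2 or Day 3. What then happens to that patient's target area depends on its outcome: healed at discharge, it enters the analysis as complete; unhealed, it leaves the analysis and another area takes its place.

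The study is unblinded and not randomized, and no control group is described (4.1, 8.2). All inference comes from change over days within the analysed areas, so nothing offsets a rule that removes short-stay failures and keeps short-stay successes. The other loss is practical: unhealed short-stay areas are enrolled, treated, photographed and then discarded.

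**Working it through.** **1. The plan's own figure.** Section 8.1 gives a difference of 10 on the VAS pain scale, SD 30, α = .0083, 80% power and a paired Wilcoxon test. Sidedness is not stated; two-sided is assumed here. A paired t-test with the noncentral t distribution needs n = 113. Dividing by the Wilcoxon efficiency for normal data, 3/π, gives 113 × π/3 = 118.3, so 119. (Searching directly on the adjusted n gives 118; power at 119 is 80.5%.) The figure of 119 reproduces, and this point does not affect it.

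**2. What happens to an area whose patient leaves before Day 5.**

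| State at discharge | 5.4, 6.3 and 8.1 | 8.3 read literally |
|---|---|---|
| Healed | kept as complete | excluded: five days not completed |
| Not healed | withdrawn and replaced | excluded |

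The middle column gives outcome-dependent selection. The right-hand column gives none by this route, but it contradicts 5.4 on early healers.

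**3. Size under 5.4, 6.3 and 8.1.** The documents give no length of stay, discharge rate or healing rate, so these inputs are assumptions:
- s = share of areas whose patient leaves before Day 5: 10–30%
- hs = share of those healed before leaving: 20–30%
- h5 = share of all areas that would heal by Day 5 if followed: 40–50%

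Formulas: kept = (1 − s) + s·hs; healed share among analysed = [(1 − s)·h5 + s·hs] / kept; areas to enrol = 119 / kept, rounded up.

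| s | hs | h5 | Kept | Healed among analysed | Inflation over h5 | Areas to enrol |
|---|---|---|---|---|---|---|
| 10% | 20% | 40% | 0.92 | 0.38/0.92 = 41.3% | 1.3 points | 129.3 → 130 |
| 10% | 30% | 50% | 0.93 | 0.48/0.93 = 51.6% | 1.6 points | 128.0 → 128 |
| 30% | 20% | 40% | 0.76 | 0.34/0.76 = 44.7% | 4.7 points | 156.6 → 157 |
| 30% | 30% | 50% | 0.79 | 0.44/0.79 = 55.7% | 5.7 points | 150.6 → 151 |

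Here s counts every early leaver. Only those whose early departure is foreseeable at enrolment can be put down to the criterion, so these figures are an upper limit for its share.

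**4. On a planned scale.** The healed share is not an endpoint; the primary analyses compare Likert and VAS scores across days (8.9.1). As a rough translation, suppose there is no true mean VAS change, the SD of change is 30, and healed means the top hs fraction on a scale that correlates r = 0.5 to 1 with VAS change. The apparent mean improvement is then r × 30 × s × φ(z) / kept, where φ(z) is the normal density at the cut-off (0.280 for hs = 20%, 0.348 for hs = 30%).
- Low end (s = 10%, hs = 20%, r = 0.5): 0.5 × 30 × 0.1 × 0.280 / 0.92 = 0.5 points.
- High end (s = 30%, hs = 30%, r = 1): 30 × 0.3 × 0.348 / 0.79 = 4.0 points.

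The design difference is 10 points.

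**5. If 8.3 is applied literally.** Short-stay areas contribute nothing, and enrolment must be at least 119/0.9 = 132.2, so 133, up to 119/0.7 = 170. The criterion then causes waste but not this upward selection.

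**The case against.** The strongest reply is that the wording is ambiguous rather than empty. The plan uses the same phrase for the whole observation window, which healing can shorten: "Participant Duration: Up to six days". Section 6.3 uses it likewise for study materials. On that reading the treatment plan must allow the full Day 0 to Day 5 window if needed. This is a fair reading, so a reader who infers that the criterion screens nobody out goes further than the text supports. What stands is that two readings are open, no minimum is written, and screeners may differ.

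Second, 5.3 steers recruitment towards patients expected to need at least five days of treatment. That helps, but it is expressed as an ideal, sits outside the eligibility criteria, and concerns need for the textile rather than presence in hospital. A patient who needs five days but leaves on Day 2 satisfies it.

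Third, the criterion is not the root cause. The selection is produced by the replacement and completer rules in 5.4, 8.1 and 8.3, and discharge on resolution of the admitting condition often cannot be known on Day 0. A reader might infer that correcting the entry rule stops the bias at its source. It does not: unplanned discharges would still be kept if healed and replaced if not. This objection stands and limits what the wording change can achieve.

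Fourth, the direction of bias assumes that 5.4 prevails over the literal text of 8.3. Sections 5.4 and 6.3 make that the likelier intent, but the plan does not settle it.

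**Conclusion.** The point holds in a limited form. The criterion states no minimum availability and can admit areas of patients already expected to leave early. Under 5.4, 6.3 and 8.1 those areas reach the analysis only if healed, which favours the device and wastes enrolment. The criterion contributes the foreseeable part of this; the replacement and completer rules produce the rest.

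The size cannot be set from the documents. Under the assumed rates, the inflation is about 1 to 6 percentage points in a healed share that is not itself a planned endpoint, and 128 to 157 areas are enrolled for 119 analysed. These are upper limits for the criterion's own effect. The VAS translation of about 0.5 to 4 points rests on further assumptions and is only illustrative. The change is worth making because it is cheap and helps under either reading of the phrase.

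**What to change.** In the Synopsis and in 5.1, replace the phrase for up to six days with a lower bound, reworded to fit the sentence. For example: *who are expected at enrolment to remain available for all assessments from Day 0 through Day 5, or until the target area is fully healed if earlier (no discharge or transfer planned before Day 5)*.

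Because this leaves unplanned discharges untouched, also amend 5.4, 8.1 and 8.3 so that every treated target area stays in the mixed-model analysis with whatever assessments it has, instead of being replaced when unhealed at discharge. If the sponsor wants 119 areas with complete data for power, further areas can be added to the early leavers rather than substituted for them. Sections 5.4 and 8.3 must be reconciled on whether areas healed before Day 5 belong to the analysis population.

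Cost: one phrase in two places, plus edits to three sections. Patients with a known early discharge would no longer be enrolled, so recruitment may be slower, although their unhealed areas are already lost to the analysis under the current rules. The mixed-model analysis of available data relies on early discharge being explainable by the observed scores, and the plan should state that assumption.

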1.2 Schedule of Activities (SOA)

Assessments and activities [#]	Day 0	Day 1	Day 2	Day 3	Day 4	Day 5/ last day of participation [‡]	Photographic evaluation using the wound camera system
PI or qualified designee obtains informed consent	X						
PI or qualified designee carries out participant screening	X						
As part of screening, PI or qualified designee examines and documents the skin fold conditions to identify potential target area(s)	X						
PI or qualified designee collects applicable demographics and co-morbidities information	X						
PI or qualified designee collects applicable medication information	X	X	X	X	X	X	
PI or qualified designee takes photographs of target areas using the wound camera system	X	X		X		X	
PI or qualified designee assesses skin fold conditions (moisture and odor) in the target area(s)	X	X		X		X	
Participant completes a survey regarding discomfort (pain, itching, and burning) in the target area(s)	X	X		X		X	
Participant identifies the prominent type of discomfort	X	X		X		X	
HCP applies SPT to the target area(s)	X	X	X [§]	X	X [§]		

Assessments and activities [#]	Day 0	Day 1	Day 2	Day 3	Day 4	Day 5/ last day of participation [‡]	Photographic evaluation using the wound camera system
HCP completes a feedback survey regarding their experience with the SPT						X	
Participant completes a survey regarding experience with the SPT						X	
Third-party clinician assesses skin fold conditions such as erythema, maceration, denudation, and satellite lesions							X
Monitoring for adverse events	X	X	X	X	X	X	
Participant dismissal from study activities						X	

[#] Study activities will occur after informed consent has been signed, and the participant has met all the inclusion criteria and none of the exclusion criteria.

[‡] SPT will be changed if clinically warranted.

^{*}If the target area(s) heal before Day 5, all activities planned for Day 5 will be carried out on the last day of study participation.

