6.2.3.1 Feedback about the SPT

HCPs will complete a survey providing their feedback about the SPT using a VAS.

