8.7. Demographics, Variables and Covariates

Age will be collected as a continuous measure, with all participants being ≥ 18 years of age. Age will be considered for secondary analysis.

Sex will be collected as a categorical variable equal to 0 = male, 1 = female, or 2 = other. Sex will be considered for secondary analysis.

Ratings for erythema, maceration, denudation, satellite lesion, odor, and survey responses for moisture in the target areas with skinfold conditions, obtained using Likert scales, will be evaluated as categorical measures. Survey responses for discomfort, HCP feedback and participants' overall experience obtained on a VAS (1–100mm) will be evaluated as continuous measures.

Nominal variables of data collected will include the participant ID, medical history, and concomitant medications. Additional nominal information regarding date, time, and reason for additional SPT changes will be recorded in a log file and this data will be incorporated into supplemental analyses examining if results differ for participants with additional SPT changes.

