8.9. Statistical Analysis

Statistical analyses will be conducted in SAS[®] software, Version 9.4 or higher of the SAS System for Windows (Copyright © 2013 SAS Institute Inc.) or other appropriate statistical software. A p-value of $P < .05$ will be considered statistically significant.

All continuous variables will be summarized using the following descriptive statistics: (non-missing sample size), mean, standard deviation, median, maximum and minimum. The frequency and percentages (based on the non-missing sample size) of observed levels will be reported for all categorical measures. In addition, 95% confidence intervals will be calculated for all means.

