8.9.2 Analysis of Secondary Endpoints

The secondary objective of this study is to gather PI or qualified designee assessment of moisture control in the target areas, as well as to assess HCP feedback about the SPT and overall participants experience with the SPT.

Moisture level in the target areas, evaluated by the PI or qualified designee using a Likert scale, will be compared across five days of treatment using ordinal mixed models. Appropriate descriptive statistics of moisture level of product, HCP feedback about the SPT, and overall participant experience with the SPT, based on the distribution and scale of the data, will also be reported.

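### The HCP feedback survey falls due at each participant's last day, but no HCP code or method for repeat responders is stated, so the planned 95% CI will be too narrow if the same HCPs answer more than once

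*Combined protocol and SAP*

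**What the plan says.** HCP feedback on the product is the second secondary endpoint. The synopsis (section 1.1) defines it as "HCP survey responses on Day 5, regarding their feedback about the SPT, using a VAS".

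The survey is a row in the participant-level schedule (section 1.2), "HCP completes a feedback survey regarding their experience with the SPT", marked only in the column for Day 5 or the last day of participation. A footnote to that schedule ties activities to the participant: "Study activities will occur after informed consent has been signed, and the participant has met all the inclusion criteria". Sections 4.1 and 8.6.2 repeat the timing. Section 6.2.3.1 adds only that "HCPs will complete a survey providing their feedback about the SPT using a VAS". It does not say which HCP answers, how often one HCP may answer, or how many HCPs take part.

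On analysis, section 8.7 includes HCP feedback among the responses "obtained on a VAS (1–100mm) will be evaluated as continuous measures". Section 8.9 states that "95% confidence intervals will be calculated for all means". Section 8.9.2 plans no test for this endpoint; it says that descriptive statistics of "HCP feedback about the SPT, and overall participant experience with the SPT, based on the distribution and scale of the data, will also be reported". The identifiers in section 8.7 are given as follows: "Nominal variables of data collected will include the participant ID, medical history, and concomitant medications". No HCP code is named there. The only random effect in section 8.9.1 is the participant, for the Likert outcomes. The single analysis population in section 8.3 is made up of participants.

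**The concern.** The endpoint is an opinion held by staff, but the forms are generated by participants finishing the study. When one nurse fills in a form for several participants, those forms share that nurse's view of the product and are not independent. The amount of information then depends largely on the number of distinct HCPs. An interval that treats each form as a separate observation overstates the precision, and HCPs who complete many forms weigh more heavily in the mean.

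Section 3 justifies the endpoint by its possible influence on HCPs' later use of the product, so the reported precision will be read. If the forms carry no respondent code, neither the extent of repetition nor a corrected interval can be worked out after the data are in.

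**Working it through.** **The plan's own figure.** The documents give no sample size, SD, number of HCPs or precision target for the HCP survey, so there is none to reproduce. The 119 target areas come from the VAS pain comparison in section 8.1. A paired t calculation with difference 10, SD 30, two-sided alpha 0.0083 and the Wilcoxon efficiency 3/π gives 118 for 80% power, and 80.5% power at 119. That figure is consistent with the text and is not affected by this point.

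**Number of forms.** The synopsis and section 5 allow up to two target areas per enrolment. The minimum is 119 / 2 = 59.5, so 60 enrolments; the maximum is 119. One form per enrolment therefore gives 60 to 119 forms if the study runs to full size. With fewer than 60 HCPs, at least one must answer more than once.

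**Effect on the interval.** Let m be the mean number of forms per HCP and ICC the correlation between forms from one HCP.

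- Design effect: DE = 1 + (m − 1) × ICC
- Correct width / width over forms = √DE
- Actual coverage of the nominal 95% interval = 2Φ(1.96 / √DE) − 1

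The number of HCPs and the ICC are assumptions. Each range below runs from ICC 0.3 to ICC 0.7.

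| Forms | HCPs | m | DE | Width factor | Coverage |
|---|---|---|---|---|---|
| 60 | 60 | 1 | 1.00 | 1.00 | 95% |
| 60 | 40 | 1.5 | 1.15 to 1.35 | 1.07 to 1.16 | 93.2% to 90.8% |
| 60 | 20 | 3 | 1.6 to 2.4 | 1.26 to 1.55 | 87.9% to 79.4% |
| 60 | 10 | 6 | 2.5 to 4.5 | 1.58 to 2.12 | 78.5% to 64.4% |
| 119 | 40 | 2.975 | 1.59 to 2.38 | 1.26 to 1.54 | 88.0% to 79.6% |
| 119 | 10 | 11.9 | 4.27 to 8.63 | 2.07 to 2.94 | 65.7% to 49.5% |

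Worked line (60 forms, 10 HCPs): m = 60/10 = 6; DE = 1 + 5 × 0.3 = 2.5 and 1 + 5 × 0.7 = 4.5; √2.5 = 1.58 and √4.5 = 2.12.

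A lower ICC weakens the effect. At ICC 0.1 with 60 forms the factor is 1.02 with 40 HCPs and 1.22 with 10. At ICC 0 it is 1.00 throughout.

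**In millimetres (illustration).** Borrow SD 30 from the pain scale, since none is given for HCP feedback. Over 60 forms the unadjusted half-width is 1.96 × 30 / √60 = 7.6 mm. It should be 8.1 to 8.8 mm with 40 HCPs and 12.0 to 16.1 mm with 10.

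The formula takes equal numbers of forms per HCP. Uneven numbers raise the design effect.

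**The case against.** The strongest reply is that the plan leaves the survey unit unstated and does not actually prescribe repeat sampling. Section 6.2.3.1 does not rule out one form per HCP. The synopsis sets a minimum of one facility and no maximum, so many HCPs could take part. Section 8.9 gives no interval formula, so independence between forms is inferred from the absence of any other method. The endpoint is descriptive and plays no part in the sample size, the interim looks or the primary analysis. Feedback per treated participant can also be a legitimate target, because it shows how the product performed across different patients.

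Most of this stands, and it limits the point to a conditional one. It does not remove the point. The schedule as written makes a form due whenever a participant finishes, an interval is required, and nothing in the plan deals with repeats. Even if feedback per participant is the target, forms from one HCP remain correlated.

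Three stronger readings are tempting, and the documents do not support them:

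- **A few staff will answer many times, so the interval is certainly much too narrow.** Neither the number of HCPs nor the ICC is given. The factor runs from 1.0 upward, and the figures for 10 HCPs alone show only one end of that range.
- **Repeat answers cannot be linked.** The list in section 8.7 is not stated to be complete, and the survey form is not in the documents. What can be said is that no HCP identifier is named.
- **The Day 5 respondent may never have applied the product.** The schedule shows no application on Day 5, but section 6.2.2.2 has HCPs apply a fresh SPT after the assessments, which include Day 5, and section 6.3 has them remove it at the end. The schedule alone cannot carry this claim, and undocumented staff turnover cannot supply the rest. It is true that no section requires the respondent to have applied the SPT.

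**Conclusion.** The point holds conditionally and is minor. The survey is tied to each participant's last day, a 95% interval is planned for its mean, and the documents state neither an HCP identifier nor a method for repeat responders. If HCPs answer for several participants and their answers are positively correlated, an interval calculated over forms as if independent is too narrow.

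For 60 forms and an assumed ICC of 0.3 to 0.7, the correct interval is about 1.07 to 1.16 times as wide with 40 HCPs and 1.6 to 2.1 times as wide with 10. There is no change if no HCP repeats. With 119 forms the factors are larger for the same number of HCPs. These sizes rest on one form per enrolment, full enrolment, equal numbers of forms per HCP, and assumed values for both the number of HCPs and the ICC.

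The consequence is confined to the stated precision of one untested secondary endpoint. It is still worth settling before the forms are collected, because correction afterwards depends on a respondent code.

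**What to change.** 1. Put an anonymous HCP code on each survey form and add it to the variables in section 8.7.
2. State the survey unit in section 1.2, section 6.2.3.1 and the endpoint definitions, choosing one of two forms:
   - one survey per HCP who has applied the SPT, with the mean and interval based on the number of HCPs; or
   - forms per participant, with responses averaged within HCP before the interval is calculated, or with a cluster-robust or HCP random-effect interval.
3. Report the number of distinct HCPs beside the number of forms.
4. Reconcile the schedule in section 1.2 with section 6.2.2.2 on whether the SPT is applied on Day 5.

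The cost is one field on the form and a few sentences in the protocol. The downside is a smaller stated n (the number of HCPs) and a wider interval. The sample size of 119 and the primary analysis do not change.
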